6.5. Concomitant Therapy

Permitted Concomitant Medication

Body Region	Permitted Topical Treatments
Palms, soles, face, and intertriginous areas	Low or least potent (Class 6 or 7) topical corticosteroids Hydrocortisone $\leq 1\%$ and hydrocortisone acetate $\leq 1\%$ are the only topical corticosteroids permitted
Scalp	Tar preparations Salicylic acid preparations Shampoos free of corticosteroids
All body regions	Study supplied non-medicated emollient, Cetaphil [®] moisturizing cream

Prohibited Concomitant Medications

1. The following hydrocortisones are NOT permitted:
 - Hydrocortisone 17 butyrate.
 - Hydrocortisone valerate.
 - Hydrocortisone/hydrocortisone acetate with concentration higher than 1%.

2. If received any of the following treatment regimens, for any reason, are eligible providing the following minimum washout criteria are observed:

Must be discontinued for at least **12 weeks** prior to first dose of study drug:

- a. Any investigational or experimental therapy or procedure for psoriasis, psoriatic arthritis or rheumatoid arthritis;
- b. efalizumab (Raptiva[®]), secukinumab (Cosentyx) or Ixekizumab (Taltz) or other anti-IL-17, tofacitinib (Xeljanz) or treatment with apremilast (Otezla).

Must be discontinued for at least **10 weeks** prior to first dose of study drug:

- a. Adalimumab (Humira[®]);
- b. Certolizumab pegol (Cimzia[®]);
- c. Infliximab (Remicade[®]);
- d. Alefacept (Amevive[®]).

Must be discontinued for at least **4 weeks** prior to first dose of study drug:

- a. Etanercept (Enbrel[®]);
- b. Systemic treatments other than biologics that could affect psoriasis, eg, oral or injectable (eg, intraarticular, intramuscular, or intravenous) corticosteroids, retinoids, methotrexate, cyclosporine, fumaric acid derivatives, sulfasalazine, hydroxycarbamide (hydroxyurea), azathioprine, intramuscular gold;
- c. Psoralen + UVA phototherapy (PUVA).

Must be discontinued for at least **2 weeks** prior to first dose of study drug:

- a. Topical treatments that could affect psoriasis, eg, corticosteroids, tars, keratolytics, anthralin, vitamin D analogs, and retinoids.
- b. Exceptions – the following **topical treatments** are allowed: non medicated emollients for use over the whole body; low or least potent (Class 6 or 7) topical corticosteroids for the palms, soles, face, and intertriginous areas only; tar and salicylic acid preparations for the scalp only, and shampoos free of corticosteroids for the scalp only. See details in Permitted Concomitant Topical Psoriasis Treatments.
- c. UVB (narrowband or broadband) phototherapy.

3. Any cell-depleting agents including but not limited to rituximab within 12 months of first dose of study drug or 5 half-lives (if known), whichever is longer, or until lymphocyte count returns to normal, whichever is longer.
4. Any prior treatment with ustekinumab (Stelara[®]), guselkumab (gene recombinant), risankizumab (gene recombinant) or non B cell-specific lymphocyte depleting agents/therapies (eg, alemtuzumab [CamPath[®]], alkylating agents [eg, cyclophosphamide or chlorambucil], total lymphoid irradiation, etc); participants who have received rituximab or other selective B-lymphocyte depleting agents (including experimental agents) within **6 months** of first dose of study drug or 5 half-lives (if known), whichever is longer, or until lymphocyte count returns to normal, whichever is longer.
5. Participants who are likely to receive during the study any moderate-strong CYP1A2 and CYP3A4 inhibitors/inducers or CYP2D6 inhibitors or MATE substrates as listed in [Appendix 8](#).

Participants will abstain from all concomitant medications as described in [Exclusion](#) sections of the protocol and [Appendix 8](#) Prohibited Concomitant Medications.

Participants should be instructed at each visit to contact the study site investigator promptly if there are any intended changes or additions to concomitant medications.

It is recommended that participants avoid changing other prescription or non-prescription drugs, vitamins, and dietary supplements within 7 days or 5 half-lives (whichever is longer) prior to the first dose of study medication and throughout the study.

All concomitant medication taken during the study must be recorded with indication, daily dose, and start and stop dates of administration.

Medications taken after informed consent is obtained (but before the first dose of study medication) will be documented as prior medications. Medications taken after the first dose of study drug has been administered will be documented as concomitant medications.

6.5.1. Rescue Medicine

There is no rescue therapy to reverse the adverse events (AEs) observed with PF-06826647; standard medical supportive care must be provided to manage the AEs.

6.6. Dose Modification

Treatment assignment in the Extension Treatment Period will be predetermined according to the Scheme shown in [Section 1.2](#). Participants who are in the placebo, 50 mg, or 100 mg treatment arms will be assigned to either 200 mg or 400 mg PF-06826647 in the Extension Treatment Period. Allocation to either dose in the Extension Treatment Period will be based on an initial treatment assignment at randomization. No dose adjustment is allowed during the study.

6.7. Intervention after the End of the Study

No intervention will be provided to study participants at the end of the study.

7. DISCONTINUATION OF STUDY INTERVENTION AND PARTICIPANT DISCONTINUATION/WITHDRAWAL

7.1. Discontinuation of Study Intervention

In rare instances, it may be necessary for a participant to permanently discontinue the investigational product. Per the study estimands, if investigational product is permanently discontinued, the participant will proceed to Early Termination per [Schedule of Activities](#). The site will inform sponsor medical monitor or sponsor clinician if the below criteria for permanent discontinuation of the IP are triggered.

Any participant meeting discontinuation criteria must have an Early Termination visit with their first visit occurring 1 week after their last dose whenever possible and continue visits per Investigator's discretion until the event has returned to normal or baseline levels or is deemed clinically stable.

The only exception to this is when a participant specifically withdraws consent for any further contact with him or her or persons previously authorized by the participant to provide this information.

Note that discontinuation of the investigational product does not represent withdrawal from the study.

Participants experiencing a thrombotic event as part of a serious adverse event must be discontinued from further IP administration and referred to a specialist for further evaluation of possible hypercoagulable state, as per local guidelines.

ECG Changes

A participant who meets either bulleted criterion below based on the average of triplicate ECG readings will be withdrawn from the IP administration.

- QTcF >500 msec;
- Change from baseline: QTc >60 msec.

If a clinically significant finding is identified (including, but not limited to, changes from baseline in QTcF after enrollment), the investigator or qualified designee will determine if the participant can continue in the study and if any change in participant management is needed. This review of the ECG printed at the time of collection must be documented. Any new clinically relevant finding should be reported as an AE.

Laboratory Abnormalities

All the following laboratory abnormalities require discontinuation if they are confirmed.
Confirmation through re-testing should occur within 48 hours:

Laboratory Variable	Laboratory Value
Hematology	
Absolute Neutrophil Count	<1000/mm ³ ; <1.0 x10 ⁹ /L
Hemoglobin	<10.0 g/dL; <6.2 mmol/L; <100 g/L
Platelet count	<75,000/mm ³ ; <75.0x10 ⁹ /L
Lymphocytes	<500/mm ³ ; <0.5x10 ⁹ /L
Chemistry	
AST ^a	>3x ULN
ALT ^a	>3x ULN
Total bilirubin ^b	>1.5x ULN

- Additional investigations, such as review of ethanol, recreational drug and dietary supplement consumption should be done; testing for acute hepatitis A, B or C infection and biliary tract imaging should be promptly discussed with sponsor medical monitor.
- Total bilirubin >1.5 x ULN; participants with a history of Gilbert's syndrome may have a direct bilirubin measured and would be eligible for this study provided the direct bilirubin is <ULN.

Pregnancy

If pregnancy is confirmed by serum beta human chorionic gonadotropin (β -hCG) testing at any time, then the sponsor clinician or sponsor medical monitor should be notified immediately.

Suicidality

Participants triggering criteria for suicidal ideation and behavior as described in [Section 8.2.5.1](#).

See the [SoA](#) for data to be collected at the time of intervention discontinuation and follow-up and for any further evaluations that need to be completed.

7.2. Participant Discontinuation/Withdrawal from the Study

A participant may withdraw from the study at any time at his/her own request or may be withdrawn at any time at the discretion of the investigator for safety, behavioral, compliance, or administrative reasons.

At the time of discontinuing from the study, if possible, an early termination visit should be conducted. See the [SoA](#) for assessments to be collected at the time of study discontinuation and follow-up and for any further evaluations that need to be completed.

The Early Termination visit applies only to participants who are randomized and then are prematurely withdrawn from the study. Participants should be questioned regarding their reason for withdrawal. The participant will be permanently discontinued both from the study intervention and from the study at that time.

If a participant withdraws from the study, he/she may request destruction of any remaining samples, but data already generated from the samples will continue to be available and may be used to protect the integrity of existing analyses. The investigator must document any such requests in the site study records.

If the participant withdraws from the study and also withdraws consent (see below) for disclosure of future information, no further evaluations should be performed, and no additional data should be collected. The sponsor may retain and continue to use any data collected before such withdrawal of consent.

When a participant withdraws from the study because of an SAE, the SAE must be recorded on the CRF and reported on the Clinical Trial (CT) SAE Report.

Lack of completion of all or any of the withdrawal/early termination procedures will not be viewed as protocol deviations so long as the participant's safety was preserved.

For participants who discontinue early from the Investigational Treatment Period prior to the Week 16 visit, or those who discontinue early from the Extension Treatment Period prior to the Week 40 visit, should perform the procedures scheduled at the Early Termination (ET) visit.

See [Section 10](#) for Guidelines for Safety Monitoring and Discontinuations.

Withdrawal of Consent:

Participants who request to discontinue receipt of study treatment will remain in the study and proceed to ET visit as soon as possible. Whenever possible, these participants should have one visit approximately two weeks after the last dose (Week 20 or 44 Follow up visit assessments) and/or at least 28 days after the last dose of IP was administered.

The only exception to this is when a participant specifically withdraws consent for any further contact with him or her or persons previously authorized by the participant to provide this information. Participants should notify the investigator in writing of the decision to withdraw consent from future follow-up, whenever possible. The withdrawal of consent should be explained in detail in the medical records by the investigator, as to whether the withdrawal is only from further receipt of investigational product or also from study procedures and/or posttreatment study follow-up, and entered on the appropriate CRF page. In the event that vital status (whether the participant is alive or dead) is being measured, publicly available information should be used to determine vital status only as appropriately directed in accordance with local law.

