4. STUDY DESIGN

4.1. Overall Design

This is a Phase 2b, randomized, double blind, placebo controlled, parallel group, multicenter study in participants with moderate to severe plaque psoriasis. After a screening period of - up to 6 weeks, eligible participants will be randomized in a 2:1:1:2:2 ratio such that participants will receive placebo or either one of four PF-06826647 daily dose levels (50 mg, 100 mg, 200 mg or 400 mg) every day during the Investigational Treatment Period for 16 weeks in a blinded fashion. All participants completing the 16-week Investigational Period will continue to a 24-week non-placebo-controlled Extension Treatment Period with double blind oral daily treatment, if per the Investigator judgment the participant is compliant with study procedures and continued participation presents no safety risks. The participants continuing into the Extension Treatment Period that were originally randomized to the

200 mg and 400 mg treatment groups will continue their respective doses, while those randomized to one of the other treatment groups (including placebo) will be randomly assigned (at study baseline) to receive either 200 mg or 400 mg during the Extension Treatment Period. Participants who discontinue prior to Week 16 visit will have an Early Termination visit and will not be eligible for the Extension Period.

Approximately 160 participants (40 participants in each of the following arms: placebo, 200 mg, and 400 mg; and 20 participants in each of the following arms: 50 mg and 100 mg) will be randomly assigned to a treatment group in order to ensure a minimum of 128 evaluable participants completing Week 16 (assuming a 20% dropout rate).

The total duration of study participation will be approximately 50 weeks, including up to 6 weeks Screening Period, 16-week Investigational Treatment Period, the 24-week Extension Treatment Period and a Follow-Up visit 4 weeks after the Extension Treatment Period.

If a participant is withdrawn from investigational product (IP) treatment, the participant will proceed with the Early Termination (ET) and Follow Up visits per [Schedule of Activities](#).

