2.3. Schema

The total duration of study participation will be approximately 50 weeks, including up to 6 weeks Screening Period, 16 week Investigational Treatment Period, the 24 week Extension Treatment Period and a Follow-Up visit 4 weeks after the Extension Treatment Period.

Investigators, participants, and the sponsor study team (with the exception of the sponsor supply chain lead) will be blinded as to investigational drug.

If a participant is withdrawn from IP treatment, the participant will proceed with the Early Termination (ET) and Follow up visits per Schedule of Activities. If a participant uses prohibited medication, guidance in Section 10.8 of the protocol should be followed.

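### Protocol 7.2 limits the Early Termination visit to study withdrawals, against the rest of the plan, and its two-week post-treatment visit does not match the 28-day Follow-Up it names

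*Protocol*

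**What the plan says.** Protocol 7.2 opens with the study-withdrawal case: "At the time of discontinuing from the study, if possible, an early termination visit should be conducted". It then restricts the visit: "The Early Termination visit applies only to participants who are randomized and then are prematurely withdrawn from the study". It adds: "The participant will be permanently discontinued both from the study intervention and from the study at that time".

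Other text treats stopping drug and leaving the study as different things:

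- Protocol 7.1 sends anyone who permanently stops IP to ET and says: "Note that discontinuation of the investigational product does not represent withdrawal from the study".
- Protocol 4.1 says that after withdrawal from IP "the participant will proceed with the Early Termination (ET) and Follow Up visits per" the Schedule of Activities. SAP 2.3 repeats this: "the participant will proceed with the Early Termination (ET) and Follow up visits per Schedule of Activities".
- Protocol 7.2, a few paragraphs later, tells participants who leave either treatment period early to complete the ET procedures.
- Protocol 7.2, under Withdrawal of Consent, says: "Participants who request to discontinue receipt of study treatment will remain in the study and proceed to ET visit as soon as possible".

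That last paragraph then asks, whenever possible, for a single further attendance, timed as follows: "approximately two weeks after the last dose (Week 20 or 44 Follow up visit assessments) and/or at least 28 days after the last dose".

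**The concern.** A participant who stops IP but has not withdrawn consent has no single defined path. A site that follows the restrictive sentences in 7.2 could close that participant out at ET. A site that follows Protocol 4.1 would bring the same participant back for Follow-Up. Section 7.2 also says that uncompleted ET procedures are not protocol deviations so long as safety was preserved, so deviation reports may not reveal the difference.

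The post-treatment visit has a separate fault. It carries the Week 20/44 label, but one of its two permitted times is half the interval at which the Schedule places that visit.

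What could be lost is the scheduled Follow-Up contact: hematology and chemistry, vital signs, brief physical examination, urine pregnancy test and contraception check.

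**Working it through.** The plan gives no figure of its own to reproduce here. The check is a comparison of the sections followed by day arithmetic.

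**Step 1. Trace one participant who permanently stops IP and has not withdrawn consent.**

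| Source | ET visit? | Still in the study? | Follow-Up? |
|---|---|---|---|
| Protocol 7.2, restrictive sentences | No, unless withdrawn from the study | No, once at ET | None implied |
| Protocol 7.2, sentence on leaving a treatment period early | Yes | Not stated | Not stated |
| Protocol 7.2, Withdrawal of Consent | Yes, as soon as possible | Yes | One visit, about day 14 and/or day 28 or later |
| Protocol 7.1 | Yes, about 1 week after last dose | Yes | Further visits at investigator discretion |
| Protocol 4.1 and SAP 2.3 | Yes | Implied | Yes |

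The first row cannot be reconciled with the others. Reading it as confined to study withdrawals by the section title does not help. The word *only* excludes everyone else from ET, and a later paragraph under the same title gives ET to participants who stay in the study.

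**Step 2. Compare the post-treatment visit with the Schedule.** The Schedule's target days are Week 16 = Day 113, Week 20 Follow-Up = Day 141, Week 40 = Day 281 and Week 44 Follow-Up = Day 309, with ±3 days on Follow-Up.

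- Follow-Up interval: 141 − 113 = 28 days, and 309 − 281 = 28 days.
- With ±3 days around the target: 25 to 31 days.
- A visit at day 14 falls 25 − 14 = 11 days before the earliest of these.

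**Step 3. Compare it with the 28-day periods.** Adverse events are actively collected for at least 28 days after last dose (Protocol 8.3.1). Contraception is required for 28 days (Protocol 5.3.1 and 10.4.2).

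- If *and/or* is met by the two-week visit alone, the shortfall is 28 − 14 = 14 days.
- No laboratory draw is then scheduled for days 15 to 28. Protocol 8.2.4 nevertheless expects clinically significant values found within 28 days of last dose to be repeated.

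**Step 4. Example with last dose on Day 28.**

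- ET at one week: 28 + 7 = Day 35.
- Two-week visit: 28 + 14 = Day 42.
- End of the 28-day periods: 28 + 28 = Day 56.

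If Day 42 is the last visit, Days 43 to 56 have no scheduled contact. Using the Schedule's Day 141 literally would put Follow-Up 141 − 28 = 113 days after last dose. The Schedule's day count therefore does not settle the timing for an early stopper, and the interval has to be tied to last dose.

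**The case against.** The strongest reply is that ET routing is clear enough in practice. Protocol 7.1 makes ET mandatory for anyone meeting discontinuation criteria, 4.1 and SAP 2.3 give IP stoppers both visits, and 7.2 itself sends early discontinuers to the ET procedures. On that view the word *only* is a stray. This limits the consequence but leaves two incompatible instructions in an operative section.

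The second reply is that safety does not hang on this visit, and most of that stands. The 28-day collection of adverse events applies whatever visits are held (8.3.1). Events are followed through visits or contacts until resolved (8.3.3), unscheduled laboratory tests are allowed at any time (8.2), and the duty to repeat abnormal values does not depend on the calendar (8.2.4). Protocol 8.3.5.1 puts five terminal half-lives at about 7 to 11 days, so day 14 is already past that. Against this, 10.4.2 itself links the 28-day contraception period to elimination of the drug.

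A reader might infer three stronger things that the documents do not support:

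- *That the two-week sentence is what lets scheduled visits end early.* Protocol 7.1 and the ET footnote to the Schedule already leave visits after ET to investigator discretion. Early discontinuers are also barred from the Extension (4.1).
- *That the different ET timings are an error to be harmonized at one week.* An immediate visit is sensible for someone asking to stop, who may not return a week later. Delaying it could lose data.
- *That the SAP's E2 data set is wrong because, unlike the E1 set in SAP 4.4, it does not blank values after withdrawal of study drug.* Event B in SAP 2.1.2 concerns events that lead to missing data, and an observed PASI score is not missing. Protocol 9.1.1 speaks of study withdrawal, not drug withdrawal. Blanking those scores is a choice of estimand, not a correction.

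**Conclusion.** Wrong as written, with a modest consequence. Two faults stand. First, the restrictive ET and off-study sentences contradict Protocol 7.1, Protocol 4.1, later text in 7.2 and SAP 2.3. Second, the two-week option does not match the 28-day Follow-Up it is labelled as, and it can be met 14 days before the adverse event and contraception periods end.

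The exposure is limited to participants who stop IP early and whose site takes the narrower reading or the earlier visit. The documents give no basis for counting them. The visit is also requested only whenever possible, so some would not attend under any wording.

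The primary PASI 90 analysis does not change. The E1 set in SAP 4.4 counts everything after withdrawal of drug or study as failure, so the route a participant takes after stopping does not alter the result. No sample size, power or alpha figure is involved.

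**What to change.** In Protocol 7.2:

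1. Delete *only*, so that ET applies to everyone who permanently stops IP or withdraws from the study.
2. Limit the sentence that takes participants off both drug and study to those who actually withdraw from the study.
3. Replace the two-weeks and/or 28-days wording with the Follow-Up visit at least 28 days after last dose, counted from last dose. Keep ET as soon as possible for those who ask to stop and at about 1 week for others.

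In the SAP, at most add one sentence stating whether withdrawal in E2 event B includes withdrawal of study drug. No change to the E2 data set is proposed.

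The cost is a short wording amendment, which needs ethics committee approval under Protocol 10.1.1. Some IP stoppers would attend a later visit than the present text allows, but Protocol 4.1 already plans Follow-Up for them.

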7.3. Lost to Follow-up

All reasonable efforts must be made to locate participants to determine and report their ongoing status. This includes follow-up with persons authorized by the participant as noted below.

A participant will be considered lost to follow-up if he or she repeatedly fails to return for scheduled visits and is unable to be contacted by the study site.

The following actions must be taken if a participant fails to return to the clinic for a required study visit:

- The site must attempt to contact the participant and reschedule the missed visit as soon as possible and counsel the participant on the importance of maintaining the assigned visit schedule and ascertain whether or not the participant wishes to and/or should continue in the study;
- Before a participant is deemed lost to follow-up, the investigator or designee must make every effort to regain contact with the participant (where possible, 3 telephone calls and, if necessary, a certified letter to the participant's last known mailing address or local equivalent methods). These contact attempts should be documented in the participant's medical record;
- The investigator should inquire about the reason for withdrawal, request that the participant return all unused investigational product(s), request that the participant return for a final visit, if applicable, and follow up with the participant regarding any unresolved adverse events (AEs);
- Should the participant continue to be unreachable, he/she will be considered to have withdrawn from the study.

Discontinuation of specific sites or of the study as a whole is handled as part of [Appendix 1](#).

